9.5 INTERIM ANALYSES

No interim analyses are planned.

The analysis will be conducted in two steps:

- **First step: Primary analysis treatment period:**
The final analysis of the primary analysis period of the study will be conducted when all participants have completed the primary analysis period of the study. It will consist in the final analysis of the primary, secondary, and exploratory endpoints at 104 weeks. The analysis of the primary analysis period will be conducted when all participants have completed the Week 104 visit or have prematurely discontinued the study.
- **Second step: analysis of the OLE treatment period:**
The final analysis of the OLE treatment period of the study will be conducted when all participants have completed the Week 208 visit and safety follow up visit or have prematurely discontinued the study.

9.5.1 Data Monitoring Committee (DMC)

An independent DMC will be used to monitor safety of the study. Unblinded DMC reports will be prepared by an independent unblinded statistician. Timing of such reviews as well as the specific responsibilities and mode of operation of the DMC will be described in the DMC charter.

10 SUPPORTING DOCUMENTATION AND OPERATIONAL CONSIDERATIONS

10.1 APPENDIX 1: REGULATORY, ETHICAL, AND STUDY OVERSIGHT CONSIDERATIONS

10.1.1 Regulatory and ethical considerations

- This study will be conducted in accordance with the protocol and with the following:
 - Consensus ethical principles derived from international guidelines including the Declaration of Helsinki and the applicable amendments and Council for International Organizations of Medical Sciences (CIOMS) International Ethical Guidelines
 - Applicable ICH GCP Guidelines
 - Applicable laws and regulations
- The protocol, protocol amendments, ICF, Investigator Brochure, and other relevant documents (eg, advertisements) must be submitted to an IRB/IEC by the Investigator and reviewed and approved by the IRB/IEC before the study is initiated.
- Any amendments to the protocol will require IRB/IEC approval before implementation of changes made to the study design, except for changes necessary to eliminate an immediate hazard to study participants.
- The Investigator will be responsible for the following:
 - Providing written summaries of the status of the study to the IRB/IEC annually or more frequently in accordance with the requirements, policies, and procedures established by the IRB/IEC
 - Notifying the IRB/IEC of SAEs or other significant safety findings as required by IRB/IEC procedures
 - Providing oversight of the conduct of the study at the site and adherence to requirements of 21 Code of Federal Regulation (CFR), ICH guidelines, the IRB/IEC, European regulation 536/2014 for clinical studies (if applicable), and all other applicable local regulations

10.1.2 Financial disclosure

Investigators and sub-Investigators will provide the Sponsor with sufficient, accurate financial information as requested to allow the Sponsor to submit complete and accurate financial certification or disclosure statements to the appropriate regulatory authorities. Investigators are responsible for providing information on financial interests during the course of the study and for 1 year after completion of the study.

10.1.3 Informed consent process

- The Investigator or his/her representative will explain the nature of the study to the participant and/or participant's parent(s)/legal guardian(s) and answer all questions regarding the study.
- Participant and/or participant's parent(s)/legal guardian(s) must be informed that their participation is voluntary. Participant and/or participant's parent(s)/legal guardian(s) will be required to sign a statement of informed consent that meets the requirements of 21 CFR 50, local regulations, ICH guidelines, Health Insurance Portability and Accountability Act (HIPAA) requirements, where applicable, and the IRB/IEC or study center.
- The medical record must include a statement that written informed consent was obtained before the participant was enrolled in the study and the date the written consent was obtained. The authorized person obtaining the informed consent must also sign the ICF.
- Participant and/or participant's parent(s)/legal guardian(s) must be re-consented to the most current version of the ICF(s) during their participation in the study.
- A copy of the ICF(s) must be provided to the participant and/or participant's parent(s)/legal guardian(s).

Participants who are rescreened are required to sign a new ICF.

The ICF will contain a separate section that addresses the use of remaining mandatory samples for optional exploratory research. The Investigator or authorized designee will explain to each participant the objectives of the exploratory research. Participants will be told that they are free to refuse to participate and may withdraw their consent at any time and for any reason during the storage period. A separate signature will be required to document a participant's agreement to allow any remaining specimens to be used for exploratory research. Participants who decline to participate in this optional research will not provide this separate signature.

10.1.4 Data protection

All personal data collected related to participants, Investigators, or any person involved in the study, which may be included in the Sponsor's databases, shall be treated in compliance with all applicable laws and regulations including the Global Data Protection Regulation (GDPR).

Data collected must be adequate, relevant and not excessive, in relation to the purposes for which they are collected. Each category of data must be properly justified and in line with the study objective.

“Participant race and ethnicity will be collected in this study because these data are required by regulatory agencies (eg, on afro American population for the FDA or on Japanese population for the Pharmaceuticals and Medical Devices Agency in Japan)”.

- Participants will be assigned a unique identifier by the Sponsor. Any participant records or datasets that are transferred to the Sponsor will contain the identifier only; participant names or any information which would make the participant identifiable will not be transferred.

- The participant must be informed that his/her personal study-related data will be used by the Sponsor in accordance with local data protection law. The level of disclosure must also be explained to the participant.
- The participant must be informed that his/her medical records may be examined by Clinical Quality Assurance auditors or other authorized personnel appointed by the Sponsor, by appropriate IRB/IEC members, and by inspectors from regulatory authorities.
- When archiving or processing personal data pertaining to the Investigator and/or to the participants, the Sponsor shall take all appropriate measures to safeguard and prevent access to this data by any unauthorized third party.

10.1.5 Committees structure

Study committees

A DMC, operating independently from the Sponsor and Clinical Investigators, will be responsible for overseeing the safety of participants and the risk/benefit ratio throughout the study. This committee is composed of externally based individuals with expertise in the disease under study, biostatistics, and/or clinical research. The primary responsibilities of the DMC are to ensure the participant's welfare as well as to evaluate and review the safety and other applicable data throughout the course of the study and make appropriate recommendations to the Sponsor regarding the conduct of the clinical trial. The specific responsibilities of the DMC will be described in the DMC Charter.

10.1.6 Dissemination of clinical study data

Sanofi shares information about clinical trials and results on publicly accessible websites, based on company commitments, international and local legal and regulatory requirements, and other clinical trial disclosure commitments established by pharmaceutical industry associations. These websites include clinicaltrials.gov, European Union [clinicaltrialregister \(eu.ctr\)](http://clinicaltrialregister.eu), and sanofi.com, as well as some national registries.

In addition, results from clinical trials in participants are required to be submitted to peer-reviewed journals following internal company review for accuracy, fair balance and intellectual property. For those journals that request sharing of the analyzable data sets that are reported in the publication, interested researchers are directed to submit their request to clinicalstudydatarequest.com.

Individual participant data and supporting clinical documents are available for request at clinicalstudydatarequest.com. While making information available we continue to protect the privacy of participants in our clinical trials. Details on data sharing criteria and process for requesting access can be found at this web address: clinicalstudydatarequest.com.

10.1.7 Data quality assurance

- All participant data relating to the study will be recorded on printed or electronic CRF unless transmitted to the Sponsor or designee electronically (eg, laboratory data). The Investigator is responsible for verifying that data entries are accurate and correct by physically or electronically signing the CRF.
- The Investigator must maintain accurate documentation (source data) that supports the information entered in the CRF.
- The Investigator must permit study-related monitoring, audits, IRB/IEC review, and regulatory agency inspections and provide direct access to source data documents.
- Monitoring details describing strategy (eg, risk-based initiatives in operations and quality such as Risk Management and Mitigation Strategies and Analytical Risk-Based Monitoring), methods, responsibilities and requirements, including handling of noncompliance issues and monitoring techniques (central, remote, or on-site monitoring) are provided in separate study documents.
- The Sponsor or designee is responsible for the data management of this study including quality checking of the data.
- The Sponsor assumes accountability for actions delegated to other individuals (eg, Contract Research Organizations).
- Study monitors will perform ongoing source data verification to confirm that data entered into the CRF by authorized site personnel are accurate, complete, and verifiable from source documents; that the safety and rights of participants are being protected; and that the study is being conducted in accordance with the currently approved protocol and any other study agreements, ICH GCP, and all applicable regulatory requirements.
- Records and documents, including signed ICFs, pertaining to the conduct of this study must be retained by the Investigator for 25 years after the signature of the final study report unless local regulations or institutional policies require a longer retention period. No records may be destroyed during the retention period without the written approval of the Sponsor. No records may be transferred to another location or party without written notification to the Sponsor.

10.1.8 Source documents

- Source documents provide evidence for the existence of the participant and substantiate the integrity of the data collected. Source documents are filed at the Investigator's site.
- Data reported on the CRF or entered in the eCRF that are transcribed from source documents must be consistent with the source documents or the discrepancies must be explained. The Investigator may need to request previous medical records or transfer records, depending on the study. Also, current medical records must be available.
- Definition of what constitutes source data can be found in study reference manual.

10.1.9 Study and site closure

The Sponsor or designee reserves the right to close the study site or terminate the study at any time for any reason at the sole discretion of the Sponsor. Study sites will be closed upon study completion. A study site is considered closed when all required documents and study supplies have been collected and a study-site closure visit has been performed.

The Investigator may initiate study-site closure at any time, provided there is reasonable cause and sufficient notice is given in advance of the intended termination.

Reasons for the early closure of a study site by the Sponsor or Investigator may include but are not limited to:

- The information on the product leads to doubt as to the benefit/risk ratio.
- Participant enrollment is unsatisfactory.
- Noncompliance of the Investigator or Sub-Investigator, delegated staff with any provision of the clinical trial protocol, and breach of the applicable laws and regulations or breach of the ICH GCP.
- The Investigator has received from the Sponsor all IMP, means, and information necessary to perform the clinical trial and has not included any participant after a reasonable period of time mutually agreed upon.
- The total number of participants are included earlier than expected.
- If the study no longer meets the development needs of the compound or business needs of the company.

10.1.10 Publication policy

- The results of this study may be published or presented at scientific meetings. If this is foreseen, the Investigator agrees to submit all manuscripts or abstracts to the Sponsor before submission. This allows the Sponsor to protect proprietary information and to provide comments.
- The Sponsor will comply with the requirements for publication of study results. In accordance with standard editorial and ethical practice, the Sponsor will generally support publication of multicenter studies only in their entirety and not as individual site data. In this case, a coordinating Investigator will be designated by mutual agreement.
- Authorship will be determined by mutual agreement and in line with International Committee of Medical Journal Editors authorship requirements.

10.2 APPENDIX 2: CLINICAL LABORATORY TESTS

- The tests detailed in [Table 7](#) will be performed by the central laboratory, except urinalysis by dipstick and “other tests” as listed in [Table 7](#).

- , which will be performed at the study site. If local laboratory results are used to make a study treatment decision, response evaluation, or to diagnose/follow-up an AE, the results must be entered into the eCRF.
- Protocol-specific requirements for inclusion or exclusion of participants are detailed in [Section 5](#) of the protocol.
- Additional tests may be performed at any time during the study as determined necessary by the Investigator or required by local regulations.
- The first 1 to 2 mL of CSF may be discarded; the subsequent 2 to 4 mL will be processed at the site's local laboratory facility (unless the laboratory is not able to process the CSF within 4 hours) to conduct standard analyses on cell count (including red blood cell counts), protein and glucose levels. The remaining CSF will be processed and shipped to a central laboratory for biomarker and PK assessments. Further details will be in the laboratory manual provided by the central laboratory.

Table 7 - Protocol-required laboratory assessments

Laboratory assessments	Parameters
Hematology	Platelet count Red blood cell (RBC) count Hemoglobin Hematocrit RBC indices: Mean corpuscular volume (MCV) Mean corpuscular hemoglobin (MCH) % Reticulocytes White blood cell (WBC) count with differential: Neutrophils Lymphocytes Monocytes Eosinophils Basophils
Clinical chemistry ^a	Blood urea nitrogen (BUN) Creatinine, estimated glomerular filtration rate Glucose Potassium Sodium Calcium Aspartate aminotransferase (AST)/Serum glutamic-oxaloacetic transaminase (SGOT) Alanine aminotransferase (ALT)/Serum glutamic-pyruvic transaminase (SGPT)

Laboratory assessments	Parameters
	Alkaline phosphatase Total and direct bilirubin Total protein
Routine urinalysis ^b	Specific gravity pH, glucose, protein, blood, ketones, bilirubin, urobilinogen, nitrite, leukocyte esterase by dipstick Microscopic examination (if blood or protein is abnormal)
Urine biochemistry	Creatinine Total protein Albumin UPCR UACR
Other screening tests	Human chorionic gonadotropin (hCG) pregnancy test (as needed for women of childbearing potential) ^c The results of each test must be entered into the eCRF. Serology (HIV antibody, hepatitis B surface antigen (HBsAg), and hepatitis C virus antibody, other infectious disease or other tests) if locally required.

Abbreviations: eCRF, electronic case report form; IRB/IEC, Institutional Review Board/Independent Ethics Committee; SAE, serious adverse event.

NOTES :

- a Details of liver chemistry stopping criteria and required actions and follow-up assessments after liver stopping or monitoring event are given in [Section 10.6](#) (Appendix 6). All events which may indicate severe liver injury (possible Hy's Law) must be reported as an SAE (excluding studies of hepatic impairment or cirrhosis).
- b Urinalysis by dipstick will be performed at the site. If abnormal, a complete urinalysis will be performed by the central laboratory.
- c Urinalysis by dipstick will be performed at the site and home. Local urine testing will be standard for the protocol unless serum testing is required by local regulation or the IRB/IEC.

Investigators must document their review of each laboratory safety report.

10.3 APPENDIX 3: ADVERSE EVENTS: DEFINITIONS AND PROCEDURES FOR RECORDING, EVALUATING, FOLLOW-UP, AND REPORTING

DEFINITION OF AE

AE definition

- An AE is any untoward medical occurrence in a participant or clinical study participant, temporally associated with the use of study intervention, whether or not considered related to the study intervention.
- NOTE: An AE can therefore be any unfavorable and unintended sign (including an abnormal laboratory finding), symptom, or disease (new or exacerbated) temporally associated with the use of study intervention.

Events meeting the AE definition

- Any abnormal laboratory test results (hematology, clinical chemistry, or urinalysis) or other safety assessments (eg, ECG, radiological scans, vital signs measurements),

including those that worsen from baseline, considered clinically significant in the medical and scientific judgment of the Investigator (ie, not related to progression of underlying disease), eg:

- Symptomatic and/or
 - Requiring either corrective treatment or consultation, and/or
 - Leading to IMP discontinuation or modification of dosing, and/or
 - Fulfilling a seriousness criterion, and/or
 - Defined as an AESI
- Exacerbation of a chronic or intermittent pre-existing condition including either an increase in frequency and/or intensity of the condition.
 - New conditions detected or diagnosed after study intervention administration even though it may have been present before the start of the study.
 - Signs, symptoms, or the clinical sequelae of a suspected drug-drug interaction.
 - Signs, symptoms, or the clinical sequelae of a suspected overdose of either study intervention or a concomitant medication.
 - “Lack of efficacy” or “failure of expected pharmacological action” per se will not be reported as an AE or SAE. Such instances will be captured in the efficacy assessments. However, the signs, symptoms, and/or clinical sequelae resulting from lack of efficacy will be reported as AE or SAE if they fulfil the definition of an AE or SAE.
 - The signs, symptoms, and/or clinical sequelae resulting from lack of efficacy will be reported as AE or SAE if they fulfil the definition of an AE or SAE. Also, “lack of efficacy” or “failure of expected pharmacological action” also constitutes an AE or SAE.

Events NOT meeting the AE definition

- Any clinically significant abnormal laboratory findings or other abnormal safety assessments which are associated with the underlying disease, unless judged by the Investigator to be more severe than expected for the participant’s condition.
- The disease/disorder being studied or expected progression, signs, or symptoms of the disease/disorder being studied, unless more severe than expected for the participant’s condition.
- Medical or surgical procedure (eg, endoscopy, appendectomy): the condition that leads to the procedure is the AE.
- Situations in which an untoward medical occurrence did not occur (social and/or convenience admission to a hospital).
- Anticipated day-to-day fluctuations of pre-existing disease(s) or condition(s) present or detected at the start of the study that do not worsen.

DEFINITION OF SAE

If an event is not an AE per definition above, then it cannot be an SAE even if serious conditions are met (eg, hospitalization for signs/symptoms of the disease under study, death due to progression of disease).

A SAE is defined as any untoward medical occurrence that, at any dose:

A) Results in death

B) Is life-threatening

The term “life-threatening” in the definition of “serious” refers to an event in which the participant was at risk of death at the time of the event. It does not refer to an event, which hypothetically might have caused death, if it were more severe.

C) Requires inpatient hospitalization or prolongation of existing hospitalization

In general, hospitalization signifies that the participant has been detained (usually involving at least an overnight stay) at the hospital or emergency ward for observation and/or treatment that would not have been appropriate in the physician’s office or outpatients setting. Complications that occur during hospitalization are AEs. If a complication prolongs hospitalization or fulfills any other serious criteria, the event is serious. When in doubt as to whether “hospitalization” occurred or was necessary, the AE should be considered serious.

Hospitalization for elective treatment of a pre-existing condition that did not worsen from baseline is not considered an AE.

D) Results in persistent disability/incapacity

- The term disability means a substantial disruption of a person’s ability to conduct normal life functions.
- This definition is not intended to include experiences of relatively minor medical significance such as uncomplicated headache, nausea, vomiting, diarrhea, influenza, and accidental trauma (eg, sprained ankle) which may interfere with or prevent everyday life functions but do not constitute a substantial disruption.

E) Is a congenital anomaly/birth defect

F) Other situations:

- Medical or scientific judgment should be exercised in deciding whether SAE reporting is appropriate in other situations such as important medical events that may not be immediately life-threatening or result in death or hospitalization but may jeopardize the participant or may require medical or surgical intervention to prevent one of the other outcomes listed in the above definition. These events should usually be considered serious.
- Examples of such events include invasive or malignant cancers, intensive treatment in an emergency room or at home for allergic bronchospasm, blood dyscrasias or convulsions that do not result in hospitalization, or development of drug dependency or drug abuse.

RECORDING AND FOLLOW-UP OF AE AND/OR SAE

AE and SAE recording

- When an AE/SAE occurs, it is the responsibility of the Investigator to review all documentation (eg, hospital progress notes, laboratory reports, and diagnostics reports) related to the event.
- The Investigator will then record all relevant AE/SAE information in the eCRF.
- It is **not** acceptable for the Investigator to send photocopies of the participant's medical records to the Sponsor or its designee in lieu of completion of the AE/SAE eCRF page.
- There may be instances when copies of medical records for certain cases are requested by the Sponsor or its designee. In this case, all participant identifiers, with the exception of the participant number, will be redacted on the copies of the medical records before submission to the Sponsor or its designee.
- The Investigator will attempt to establish a diagnosis of the event based on signs, symptoms, and/or other clinical information. Whenever possible, the diagnosis (not the individual signs/symptoms) will be documented as the AE/SAE.

Assessment of intensity

The Investigator will make an assessment of intensity for each AE and SAE reported during the study and assign it to 1 of the following categories:

- **Mild:** An event that is easily tolerated by the participant, causing minimal discomfort and not interfering with everyday activities.
- **Moderate:** An event that causes sufficient discomfort and interferes with normal everyday activities.
- **Severe:** An event that prevents normal everyday activities. An AE that is assessed as severe should not be confused with a SAE. Severe is a category utilized for rating the intensity of an event; and both AEs and SAEs can be assessed as severe.

An event is defined as "serious" when it meets at least 1 of the predefined outcomes as described in the definition of an SAE, NOT when it is rated as severe.

Assessment of causality

- The Investigator is obligated to assess the relationship between study intervention and each occurrence of each AE/SAE.
- A "reasonable possibility" of a relationship conveys that there are facts, evidence, and/or arguments to suggest a causal relationship, rather than a relationship cannot be ruled out.
- The Investigator will use clinical judgment to determine the relationship.
- Alternative causes, such as underlying disease(s), concomitant therapy, and other risk factors, as well as the temporal relationship of the event to study intervention administration will be considered and investigated.

- The Investigator will also consult the Investigator's Brochure (IB) and/or Product Information, for marketed products, in his/her assessment.
- For each AE/SAE, the Investigator **must** document in the medical notes that he/she has reviewed the AE/SAE and has provided an assessment of causality.
- There may be situations in which an SAE has occurred and the Investigator has minimal information to include in the initial report to the Sponsor or its designee. However, **it is very important that the Investigator always make an assessment of causality for every event before the initial transmission of the SAE data to the Sponsor or its designee.**
- The Investigator may change his/her opinion of causality in light of follow-up information and send a SAE follow-up report with the updated causality assessment.
- The causality assessment is one of the criteria used when determining regulatory reporting requirements.

Follow-up of AEs and SAEs

- The Investigator is obligated to perform or arrange for the conduct of supplemental measurements and/or evaluations as medically indicated or as requested by the Sponsor or its designee to elucidate the nature and/or causality of the AE or SAE as fully as possible. This may include additional laboratory tests or investigations, histopathological examinations, or consultation with other health care professionals.
- If a participant dies during participation in the study or during a recognized follow-up period, the Investigator will provide the Sponsor or its designee with a copy of any postmortem findings including histopathology.
- New or updated information will be recorded in the originally completed eCRF.
- The Investigator will submit any updated SAE data to the Sponsor or its designee within 24 hours of receipt of the information.

REPORTING OF SAES

SAE reporting to the Sponsor or its designee via an electronic data collection tool

- The primary mechanism for reporting an SAE to the Sponsor or its designee will be the electronic data collection tool.
- If the electronic system is unavailable, then the site will use the paper SAE data collection tool (see next section) in order to report the event within 24 hours.
- The site will enter the SAE data into the electronic system as soon as it becomes available.
- After the study is completed at a given site, the electronic data collection tool will be taken off-line to prevent the entry of new data or changes to existing data.
- If a site receives a report of a new SAE from a study participant or receives updated data on a previously reported SAE after the electronic data collection tool has been taken off-line, then the site can report this information on a paper SAE form (see next section) or to the Sponsor or its designee by telephone.
- Contacts for SAE reporting can be found in study reference manual.

SAE reporting to the Sponsor or its designee via paper CRF

- Facsimile transmission of the SAE paper CRF is the preferred method to transmit this information to the Sponsor or its designee.
- In rare circumstances and in the absence of facsimile equipment, notification by telephone is acceptable with a copy of the SAE data collection tool sent by overnight mail or courier service.
- Initial notification via telephone does not replace the need for the Investigator to complete and sign the SAE CRF pages within the designated reporting time frames.
- Contacts for SAE reporting can be found in study reference manual.

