7 DISCONTINUATION OF STUDY INTERVENTION AND PARTICIPANT DISCONTINUATION/WITHDRAWAL

7.1 DISCONTINUATION OF STUDY INTERVENTION

7.1.1 Definitive discontinuation

The IMP should be continued whenever possible.

In case the IMP is stopped, it should be determined whether the stop can be made temporarily. In rare instances, it may be necessary for a participant to permanently discontinue study intervention before the end of treatment visit. If study intervention is permanently discontinued, the participant will remain in the study to be evaluated for safety and efficacy. See the SoA ([Section 1.3](#)) for data to be collected at the time of discontinuation of study intervention.

Definitive intervention discontinuation is any intervention discontinuation associated with the definitive decision from the Investigator not to re-expose the participant to the IMP at any time during the study, or from the participant not to be re-exposed to the IMP due to whatever the reason.

The following may be justifiable reasons for the Investigator or Sponsor to discontinue a participant from treatment:

Participant specific:

- The participant experiences 2 similar SAEs or 1 life-threatening SAE (assessed as related by the Investigator and/or the Sponsor).
- The participant meets criteria for Hy's law (confirmed ALT $>5 \times$ ULN range or confirmed ALT $>3 \times$ ULN and bilirubin $>2 \times$ ULN).
- The participant is no longer deriving a therapeutic/clinical benefit in the opinion of the Investigator.
- The participant develops grade 3 cataract or higher.
- The participant becomes pregnant.

Study specific:

- Any AEs, per Investigator judgment, that may jeopardize the participant's safety.
- Any use of prohibited concomitant treatment (see [Section 6.5.1](#)).
- At participant's request, ie, withdrawal of the consent for treatment.

Discontinuation of study intervention for abnormal liver function should be considered by the Investigator when a participant meets one of the conditions outlined in Appendix 6 ([Section 10.6](#)) or if the Investigator believes that it is in best interest of the participant.

See the SoA for data to be collected at the time of intervention discontinuation and follow-up and for any further evaluations that need to be completed.

Any clinically significant abnormal laboratory value or ECG parameter will be immediately rechecked for confirmation before making a decision of definitive discontinuation of the IMP for the concerned participant.

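### Protocol Appendix 3 says in two adjacent bullets that lack of efficacy in itself is not, and is, an AE or SAE

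*Protocol*

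**What the plan says.** Protocol Section 8.3 sends the investigator to Appendix 3 (Section 10.3) for the definitions of AE and SAE, so the appendix is the controlling text. Two consecutive bullets in its list of events that meet the AE definition deal with lack of efficacy, or failure of the drug to act as expected.

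- The first says that this "per se will not be reported as an AE or SAE", and adds: "Such instances will be captured in the efficacy assessments". It then says that "clinical sequelae resulting from lack of efficacy will be reported as AE or SAE if they fulfil the definition of an AE or SAE".
- The second repeats the sentence on clinical consequences and ends by saying that lack of efficacy "also constitutes an AE or SAE".

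Three other statements bear on the point.

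- The list of events that do not meet the AE definition includes "The disease/disorder being studied or expected progression, signs, or symptoms of the disease/disorder being studied, unless more severe than expected" for that participant.
- The SAE definition opens with the rule: "If an event is not an AE per definition above, then it cannot be an SAE even if serious conditions are met".
- Section 7.1.1 gives among the possible reasons for stopping treatment: "The participant is no longer deriving a therapeutic/clinical benefit in the opinion of the Investigator".

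SAP Section 3.6.2 tabulates what sites report as the number and percentage of participants with at least one event. It has no rule for lack-of-efficacy entries.

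**The concern.** A reporting definition has to give one answer, and on lack of efficacy in itself this one gives two. Around 30 sites are planned. A site that reads the first bullet makes no AE entry, while a site that reads the second makes one. Both can say that they followed the protocol, and monitoring cannot call either wrong.

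The situation can be foreseen here. The disease is progressive, treatment in the primary period lasts 104 weeks against placebo, and loss of benefit is a named ground for stopping. What is at stake is whether the AE tables are comparable across sites, and whether an efficacy judgment finds its way into a safety table.

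**Working it through.** No sample size, power, error rate or event count enters this point, so there is no plan figure to reproduce. The check sets the texts side by side.

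| Question | First bullet | Second bullet |
|---|---|---|
| Is lack of efficacy in itself an AE or SAE? | No | Yes |
| Where is it captured? | Efficacy assessments | By implication, as an AE or SAE |
| Are its clinical consequences reportable? | Yes, if they meet the definition | Yes, if they meet the definition |
| Limited by population, period or arm? | No | No |

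**Step 1: can both be followed?** Not on the first row. Neither bullet carries a condition that would assign it to different cases. One might try to carry the condition in the second bullet's opening sentence (reportable if the definition is met) over to its last sentence. But that last sentence states no condition, and the first bullet still excludes lack of efficacy in itself outright.

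**Step 2: what depends on the choice?** The third row is the same in both columns. A new or worsened sign or symptom is therefore handled in the same way under either bullet. Ordinary decline is governed by the separate exclusion of expected progression. Only a bare entry of lack of efficacy is left in dispute.

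**Step 3: follow one case through.** Suppose that an investigator stops treatment because the participant no longer benefits, with no reportable sign or symptom.

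- Under the first bullet there is no AE. Because an event that is not an AE cannot be an SAE, there is no SAE either. The case appears only in the disposition summary of reasons for stopping (SAP Section 5.2).
- Under the second bullet there is an AE. If dated at the stop, it falls in the treatment-emergent period of SAP Section 3.1. It then counts in the any-TEAE overview and in the table of TEAEs that led to permanent discontinuation (SAP Table 10).

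**Step 4: what about SAEs?** Even under the second bullet, Appendix 3 asks for a seriousness criterion such as death, hospitalization or disability. A bare lack-of-efficacy entry would rarely meet one, so the 24-hour reporting duty in Section 8.3.1 is seldom reached.

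**Step 5: scale per participant.** At the planned sizes of 19 on placebo and 38 on venglustat, and assuming that all are dosed, one more participant counted moves a percentage by 1/19 = 5.3 points on placebo and 1/38 = 2.6 points on venglustat. These are units of movement, not estimates of effect. The tables count participants, so a bare entry changes a row only if that participant has no other event in it.

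**The case against.** The strongest case on the other side is that this is a drafting slip with little consequence. Most of that stands.

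- SAP Section 3.6 makes the safety analysis descriptive, with no testing, and neither co-primary endpoint uses AE data.
- AEs are coded and shown by preferred term, so lack-of-efficacy entries can be seen in the detailed tables. They would still be merged into the any-TEAE overview.
- Stops for lost benefit are recorded in the disposition summary whichever bullet a site follows.
- The list of events that do not meet the definition adds no second contradiction. It does not mention lack of efficacy, and it gives one rule for expected progression.

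A reader might also infer something stronger: that because decline is expected without treatment, the conflict could put anywhere from none to most of the placebo arm into the AE and SAE counts. The documents do not support this. Decline itself is covered by the exclusion of expected progression, and its clinical consequences are handled alike under both bullets. No expected number of lack-of-efficacy reports is given anywhere. Investigators are blinded to arm in the primary population. Bare entries might still be more frequent on placebo if the drug works, but nothing in the documents allows that to be sized.

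None of this supplies the missing rule. The two bullets still disagree.

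**Conclusion.** The contradiction is direct, current and unresolved, and its reach is narrow. It concerns only lack of efficacy in itself. It can make the descriptive counts of any TEAE, and of TEAEs leading to permanent discontinuation, depend on which bullet a site follows.

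The size cannot be derived from the documents. It is probably small, on the assumption that bare lack-of-efficacy entries are uncommon and that many such participants have another TEAE in any case. The effect on SAE counts is smaller still, since a seriousness criterion must also be met. No hypothesis test or co-primary result is affected. The point is worth correcting because the rule cannot be followed as written and the correction costs little.

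**What to change.** - **Protocol Section 10.3.** Reconcile the two bullets into one rule on lack of efficacy in itself, and state the sentence on clinical consequences once. The rule must also agree with the list of events that do not meet the AE definition. If it counts lack of efficacy as an AE, the text must say how that differs from expected progression.
- **Sites.** Send one notice giving the rule and the date from which it applies.
- **Before database lock.** Search the recorded AE terms for lack-of-efficacy entries and handle them uniformly under the rule, without reference to treatment arm. If the rule counts such events, also check treatment stops attributed to lost benefit, so that sites that made no entry are treated in the same way. Record the convention in SAP Section 3.6.2.

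The cost is a short text edit, a site notice and one data review. The edit is a protocol amendment needing ethics committee approval (Section 10.1.1), so it can go with the next amendment. Endpoints, sample size and analysis models do not change.
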